4.2.8 Anti-hypertensives

Patients who develop hypertension while on protocol therapy may be treated with anti-hypertensive agents and may remain on protocol therapy as long as hypertension is well controlled on medication. The algorithms in [Section 5.2.5](#) will be used to grade and manage axitinib-related hypertension.

4.2.9 CYP3A4 Inhibitors and Inducers

Axitinib is a major substrate for cytochrome P-450 3A4 isozyme. Strong inducers or inhibitors of CYP3A4 may alter the pharmacokinetics of axitinib and should be avoided for 7 days prior to enrollment. They should also be avoided for the duration of protocol therapy for patients in Arms A and B. Moderate inducers or inhibitors of CYP3A4 should be avoided as well, if reasonable alternatives exist. Please see [Appendix VI](#) for list of CYP3A4 inducers and inhibitors. Because the lists of these agents are constantly changing, it is important to regularly consult frequently updated medical references.

4.3 Arm A: Axitinib + Nivolumab

4.3.1 Therapy Delivery Map – Arm A: Axitinib + Nivolumab

Each cycle lasts 28 days (4 weeks). Absent disease progression or unacceptable toxicity, patients may continue on protocol therapy for up to 2 years duration or completion of 26 cycles, whichever comes first.

This TDM is on 3 pages. A copy of this TDM will be used for each cycle; please enter the cycle # below.

Patient COG ID number

DOB

Criteria to start each cycle: ANC \geq 1000/ μ L, platelet count \geq 75,000/ μ L without transfusion support. See [Section 5.0](#) for other requirements related to any ongoing toxicities.

DRUG	ROUTE	DOSAGE		DAYS	IMPORTANT NOTES
Axitinib (IND# [REDACTED]) Do not use commercial supply	PO	If \geq 18 years old: 5 mg/dose BID ^{^+}		1 – 28	[^] Dose is BID. For example, if age $<$ 18 years old, administer 2.4 mg/ m^2 /dose BID. The total daily dose is 4.8 mg/ m^2 /day, divided BID (maximum starting dose is 5 mg/dose BID). ⁺ See Section 4.3.3 for dose titration guidelines.
		If $<$ 18 years old: 2.4 mg/ m^2 /dose (max 5 mg/dose) BID ^{^+}			
Nivolumab (IND# [REDACTED]) Do not use commercial supply	IV over 30 minutes, or per institutional guidelines	240 mg/dose	OR	1, 15	For patients \geq 18 years old: Either 240 mg/dose administered on Day 1 and 15 OR 480 mg/dose administered on Day 1 only.
		If \geq 18 years old: 480 mg/dose		1 only	
		If $<$ 18 years old: 3 mg/kg/dose		1, 15	For patients $<$ 18 years old: Maximum dose is 240 mg/dose administered on Days 1 and 15.

Enter Cycle #: _____

Ht _____ cm

Wt _____ kg

BSA _____ m²

Date Due	Date Given	Day	Axitinib mg AM and mg PM	Nivolumab mg	Cycle 1 Studies	Cycles 2 - 26 studies
Enter calculated dose above and actual dose administered below						
		1	mg mg	mg	a – o, p %, q – s	a – o, p %, q – s
		2	mg mg			
		3	mg mg			
		4	mg mg			
		5	mg mg			
		6	mg mg			
		7	mg mg			
		8	mg mg		a*, c*, d – g	
		9	mg mg			
		10	mg mg			
		11	mg mg			
		12	mg mg			
		13	mg mg			
		14	mg mg			
		15	mg mg	mg [#]	a, c – g	(c – g)*
		16	mg mg			
		17	mg mg			
		18	mg mg			
		19	mg mg			
		20	mg mg			
		21	mg mg			
		22	mg mg		a*, c*, d – g	
		23	mg mg			
		24	mg mg			
		25	mg mg			
		26	mg mg			
		27	mg mg			
		28	mg mg			t
		29	Begin next cycle on Day 29 or when criteria to begin cycle are met, whichever occurs later. See Section 4.3.3 . See Section 7.0 for end of treatment evaluations.			* For patients $<$ 18 years of age only.

[#] Day 15 nivolumab does not apply to patients \geq 18 years of age, receiving 480 mg/dose on Day 1 only.

[%] Required pharmacokinetics only applies to pediatric patients (age $<$ 18 years old).

^{*}Cycles 2 and 3 only. Patients should be instructed to hold the AM axitinib dose until after the pre-dose PK has been drawn. See [Section 5.0](#) for Dose Modifications for Toxicities.

4.3.2 Required Observations in Arm A: Axitinib + Nivolumab

All baseline studies must be performed prior to starting protocol therapy unless otherwise indicated below.

- a. Physical Exam: Prior to each cycle, and additionally during Cycle 1:
 - For patients < 18 years old, perform weekly
 - For patients ≥ 18 years old, perform every other week
- b. Height/Weight: Prior to each cycle.
- c. CBC/diff/platelets: Prior to each dose of nivolumab, and additionally during Cycle 1:
 - For patients < 18 years old, perform weekly
 - For patients ≥ 18 years old, perform every other week
- d. Creatinine, bilirubin: Prior to each dose of nivolumab, weekly during Cycle 1 only.
- e. Electrolytes, BUN, Ca²⁺, PO₄, Mg²⁺: Prior to each dose of nivolumab, weekly during Cycle 1 only.
- f. AST/ALT/Albumin: Prior to each dose of nivolumab, weekly during Cycle 1 only.
- g. Blood Pressure: Prior to each dose of nivolumab, weekly during Cycle 1 only. For pediatric patients who are dose escalated, weekly monitoring for the first cycle at the higher dose will be required (See [Section 5.2.5.4](#))
- h. PT/INR: Prior to every odd-numbered cycle (e.g., Cycles 1, 3, 5, etc.).
- i. TSH: Prior to every odd-numbered cycle (e.g., Cycles 1, 3, 5, etc.).
- j. Urinalysis/Urine Protein/Creatinine: Prior to Cycles 1, 2, 3 and then prior to every odd-numbered cycle (e.g., Cycles 5, 7, 9, etc.).
- k. Lipase: Prior to each cycle.
- l. Pregnancy Test: Female patients of childbearing potential require a negative pregnancy test within 72 hours prior to starting treatment and then prior to every odd-numbered cycle (e.g., Cycles 3, 5, 7, etc.); sexually active patients must use an acceptable method of birth control.
- m. ECG: Prior to every 4th cycle starting Cycle 1 (e.g., Cycles 1, 5, 9, etc.).
- n. MUGA or ECHO: Prior to every 4th cycle starting Cycle 1 (e.g., Cycles 1, 5, 9, etc.).
- o. GFR or Creatinine Clearance: Prior to every 4th cycle starting Cycle 1 (e.g., Cycles 1, 5, 9, etc.). See [Appendix VII](#) for GFR calculation.
- p. Required Pharmacokinetics (for pediatric patients only): At 2, 4, and 6 hours post-axitinib AM dose during Cycle 1, Day 1. Additionally, pre-dose of axitinib on Day 1 of Cycles 2 and 3. For pediatric patients on Arm C that crossover to Arm A, required PK will be obtained at 2, 4 and 6 hours post-axitinib AM dose after the first dose of axitinib is given, and then pre-dose of axitinib on Days 1 of the second and third cycles of combination therapy received. **NOTE:** The first cycle of combination therapy after cross-over will be defined as the cycle for which > 14 days of axitinib is given, with Day 1 of Cycle 1 after cross-over defined as the day of first nivolumab dose during that cycle after axitinib is started or on the day axitinib is started if given concurrently. See [Section 15.1](#) for complete details.
- q. Immune biomarkers (patient consent is required): Before treatment initiation and before Day 1 of Cycles 2, 3, and 9 (within 72 hours prior to Day 1 dosing), and within 3 weeks after the last dose of study treatment. See [Section 15.2.1](#) for complete details.
- r. Tumor Tissue (patient consent is required): Before treatment initiation and at any time tumor tissue is obtained (i.e. surgery). See [Section 15.2.2](#) for complete details.
- s. Specimens for Banking (patient consent is required): See [Section 15.2.3](#) for complete details.
- t. Tumor Imaging: After Cycles 2, 4, 6, 9, 12, and then every 4 cycles; at relapse. For patients who cross-over from Arm C to Arm A at initial progression, then for the purpose

of imaging timing, the cycle number should restart at progression to "Cycle 1". See [Section 16.2](#) for complete details.

This listing only includes evaluations necessary to answer the primary and secondary aims. OBTAIN OTHER STUDIES AS REQUIRED FOR GOOD CLINICAL CARE.

Comments

(Include any held doses, or dose modifications)

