1.2 Secondary Aim

1.2.1 To further define the toxicities of the study arms in the treatment of translocation morphology RCC across all ages.

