4.4.2 Required Observations in Arm B: Axitinib

All baseline studies must be performed prior to starting protocol therapy unless otherwise indicated below.

- a. Physical Exam: Prior to each cycle, and additionally during Cycle 1:
For patients < 18 years old, perform weekly
For patients ≥ 18 years old, perform every other week
- b. Height/Weight: Prior to each cycle.
- c. CBC/diff/platelets: Prior to each cycle, and additionally during Cycle 1:
For patients < 18 years old, perform weekly
For patients ≥ 18 years old, perform every other week
- d. Creatinine, bilirubin: Prior to each cycle, weekly during Cycle 1 only.
- e. Electrolytes, BUN, Ca²⁺, PO₄, Mg²⁺: Prior to each cycle, weekly during Cycle 1 only.
- f. AST/ALT/Albumin: Prior to each cycle, weekly during Cycle 1 only.
- g. Blood Pressure: Every other week, weekly during Cycle 1 only. For pediatric patients who are dose escalated, weekly monitoring for the first cycle at the higher dose will be required (See [Section 5.2.5.4](#))
- h. PT/INR: Prior to every odd-numbered cycle (e.g., Cycles 1, 3, 5, etc.).
- i. TSH: Prior to every odd-numbered cycle (e.g., Cycles 1, 3, 5, etc.).
- j. Urinalysis/Urine Protein/Creatinine: Prior to Cycles 1, 2, 3, and then prior to every odd-numbered cycle (e.g., Cycles 5, 7, 9 etc.).
- k. Lipase: Prior to each cycle.
- l. Pregnancy Test: Female patients of childbearing potential require a negative pregnancy test within 72 hours prior to starting treatment and then prior to every odd-numbered cycle (e.g., Cycles 3, 5, 7, etc.); sexually active patients must use an acceptable method of birth control.
- m. ECG: Prior to every 4th cycle starting Cycle 1 (e.g., Cycles 1, 5, 9, etc.).
- n. MUGA or ECHO: Prior to every 4th cycle starting Cycle 1 (e.g., Cycles 1, 5, 9, etc.).
- o. GFR or Creatinine Clearance: Prior to every 4th cycle starting Cycle 1 (e.g., Cycles 1, 5, 9, etc.). See [Appendix VII](#) for GFR calculation.
- p. Immune biomarkers (patient consent is required): Before treatment initiation and before Day 1 of Cycles 2, 3, and 9 (within 72 hours prior to Day 1 dosing), and within 3 weeks after the last dose of study treatment. See [Section 15.2.1](#) for complete details.
- q. Tumor Tissue (patient consent is required): Before treatment initiation and at any time tumor tissue is obtained (i.e. surgery). See [Section 15.2.2](#) for complete details.
- r. Specimens for Banking (patient consent is required): See [Section 15.2.3](#) for complete details.

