4.5.2 Required Observations in Arm C: Nivolumab

All baseline studies must be performed prior to starting protocol therapy unless otherwise indicated below.

- a. Physical Exam: Prior to each cycle, and additionally during Cycle 1:
 - For patients < 18 years old, perform weekly
 - For patients \geq 18 years old, perform every other week
- b. Height/Weight: Prior to each cycle.
- c. CBC/diff/platelets: Prior to each dose of nivolumab, and additionally during Cycle 1:
 - For patients < 18 years old, perform weekly
 - For patients \geq 18 years old, perform every other week
- d. Creatinine, bilirubin: Prior to each dose of nivolumab, weekly during Cycle 1 only.
- e. Electrolytes, BUN, Ca^{2+} , PO_4^{3-} , Mg^{2+} : Prior to each dose of nivolumab, weekly during Cycle 1 only.
- f. AST/ALT/Albumin: Prior to each dose of nivolumab, weekly during Cycle 1 only.
- g. PT/INR: Prior to every odd-numbered cycle (e.g., Cycles 1, 3, 5, etc.).
- h. TSH: Prior to every odd-numbered cycle (e.g., Cycles 1, 3, 5, etc.).
- i. Urinalysis/Urine Protein/Creatinine: Prior to Cycles 1, 2, 3 and then prior to every odd-numbered cycle (e.g., Cycles 5, 7, 9, etc.).
- j. Lipase: Prior to each cycle.
- k. Pregnancy Test: Female patients of childbearing potential require a negative pregnancy test within 72 hours prior to starting treatment and then prior to every odd-numbered cycle (e.g., Cycles 3, 5, 7, etc.); sexually active patients must use an acceptable method of birth control.
- l. ECG: Prior to every 4th cycle starting Cycle 1 (e.g., Cycles 1, 5, 9, etc.).
- m. MUGA or ECHO: Prior to every 4th cycle starting Cycle 1 (e.g., Cycles 1, 5, 9, etc.).
- n. GFR or Creatinine Clearance: As clinically indicated. See [Appendix VII](#) for GFR calculation.
- o. Immune biomarkers (patient consent is required): Before treatment initiation and before Day 1 of Cycles 2, 3, and 9 (within 72 hours prior to Day 1 dosing), and within 3 weeks after the last dose of study treatment. See [Section 15.2.1](#) for complete details.
- p. Tumor Tissue (patient consent is required): Before treatment initiation and at any time tumor tissue is obtained (i.e. surgery). See [Section 15.2.2](#) for complete details.
- q. Specimens for Banking (patient consent is required): See [Section 15.2.3](#) for complete details.
- r. Tumor Imaging: After Cycles 2, 4, 6, 9, 12, and then every 4 cycles; at relapse. See [Section 16.2](#) for complete details.

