This listing only includes evaluations necessary to answer the primary and secondary aims. OBTAIN OTHER STUDIES AS REQUIRED FOR GOOD CLINICAL CARE.

Comments

(Include any held doses, or dose modifications)

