5.2.5.1 Baseline blood pressure (BP) is defined as the blood pressure obtained at the examination used for study enrollment. This baseline BP should be obtained as follows: (1) Obtain 2 serial blood pressures from the same extremity with the patient in the same position that are separated by at least 1 hour. Avoid using the lower extremity if possible. (2) The baseline BP is the average of the systolic measurements over the average of the diastolic measurements.

5.2.5.2 The upper limit of normal (ULN) is defined as a BP equal to the 95th percentile for age, height, and gender (see [Appendix III](#)) for patients < 18 years old, and 150/90 mmHg for patients ≥ 18 years old.

- The NCI CTCAE will be utilized to determine the grade of hypertension for reporting purposes.
- Elevated BP measurements should be repeated on the same day to confirm the elevation. Patients with elevated BP should have BP measurements performed at least twice weekly until BP is \leq ULN.
- Elevation in either systolic or diastolic blood pressure should be considered when following the algorithms below.
- Hypertension should be managed with appropriate anti-hypertensive agent(s) as clinically indicated. It is strongly recommended that nephrology or cardiology be consulted in the evaluation and management of hypertension.

5.2.5.3 **Adults (≥ 18 years of age):**

Patients/families will self-monitor BP at home twice weekly and will inform their physicians in the event of systolic BP ≥ 140 mmHg or diastolic BP ≥ 90 mmHg. In such instances, antihypertensive treatment will start or the dose of antihypertensives will be increased per physician discretion. Table 1 below provides guidelines for monitoring and managing axitinib-related hypertension in adult patients. If the patient was already on maximal antihypertensive treatment, the axitinib dose will be reduced by one dose level (see [Section 5.2.1](#)).

Table 1. Recommended Hypertension Monitoring and Management for Adult Patients

CTCAE Grade	Antihypertensive Therapy	Blood Pressure Monitoring	Dose Modification
Grade 1 – Pre-hypertension Systolic 120-139 mmHg Diastolic 80-89 mmHg		Standard	No change

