ORR: A logistic regression model for overall response, stratified by the stratification factors used at randomization (age and prior therapy) will be fit, including treatment arm as a key covariate. From this model, the odds ratio for treatment arm will be reported with a 70% confidence interval. The ORR observed within each treatment arm will also be reported.

OS: A stratified, one-sided log-rank test (using the stratification factors at randomization, age and prior therapy) will be performed to compare treatment arms with alpha = 0.15. Cox proportional hazards models will also be fit to evaluate the final hazard ratio between the treatment arms, with exploratory modeling taking into account the potential influence of other factors (e.g., baseline disease burden, upfront vs. delayed nephrectomy). From these models, the hazard ratio for treatment assignment will be reported with a 70% confidence interval (to align with the overall alpha level of the primary log-rank test).

AEs: All Grade 3 or higher non-hematologic toxicities and all Grade 4-5 adverse events occurring during protocol therapy or within 100 days of treatment discontinuation, including crossover for patients who receive crossover combination therapy, will be analyzed. The rates of these events will be reported separately by treatment arm (including crossover as a “3rd” arm for this purpose), and both by individual AE and class of AE (e.g., hematologic). Given that some AEs may be rare, Fisher Exact tests will be used to test for statistical significance among any apparent differences by treatment arm.

Exploratory Analyses

Exploratory Aim 1.3.1: To characterize tRCC clinical behavior across all age groups.
We will list and summarize the frequency of site(s) of disease at presentation (including extent of lymph node involvement), site(s) of relapse, surgical practices on protocol therapy, and radiotherapy practices on protocol therapy. We will also summarize the overall response rate (ORR) submitted by the enrolling institution.

Exploratory Aim 1.3.2: To evaluate type of antitumor immune response and stability of T cell activation before and after treatment with immunotherapy or antiangiogenic therapy.

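### Blood pressure is a scheduled on-treatment observation in Arm A but not in Arm C, so the hypertension rates that Section 9.3 compares can differ partly through ascertainment

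*Combined protocol and SAP*

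**What the plan says.** Arm A (4.3.2, item g) requires "Blood Pressure: Prior to each dose of nivolumab, weekly during Cycle 1 only", and the Arm A map in 4.3.1 carries item g on Days 1, 8, 15 and 22 of Cycle 1. Closed Arm B also had an item (4.4.2): "Blood Pressure: Every other week, weekly during Cycle 1 only". Section 5.2.5.3 adds for adults: "Patients/families will self-monitor BP at home twice weekly". That rule and the pediatric monitoring rule (5.2.5.4) both sit under dose modification for axitinib.

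The Arm C list (4.5.2, items a to r) goes from liver tests (f) to PT/INR (g), with no blood pressure item. The Arm C map shows d to f on the Cycle 1 days where Arm A shows d to g. Yet the list closes with "This listing only includes evaluations necessary to answer the primary and secondary aims", and the one secondary aim (1.2.1) is "To further define the toxicities of the study arms in the treatment of translocation morphology RCC across all ages".

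Section 9.3 reports Grade 3 or higher non-hematologic events by individual event and by arm, with cross-over patients as a third group, and says that "Fisher Exact tests will be used to test for statistical significance among any apparent differences by treatment arm". It has no caveat about unequal measurement.

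**The concern.** An asymptomatic event defined by a measurement is recorded only if someone takes the measurement. In Table 1 of 5.2.5.3, adult Grade 3 hypertension is systolic pressure of at least 160 mmHg or diastolic of at least 100 mmHg. If one arm has a fixed schedule of readings and the other has none, their recorded rates are not like for like. The same applies to an Arm C patient who crosses over, because scheduled readings begin only with Arm A therapy.

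The gap does not look like a consistent rule of omitting axitinib-related checks from Arm C. Proteinuria is also handled under axitinib dose modification (5.2.7), yet Arm C keeps Arm A's schedule for urine protein, as it does for TSH, ECG and MUGA or ECHO. Apart from axitinib pharmacokinetics, the other material difference is kidney function: every fourth cycle in Arm A, but in Arm C "GFR or Creatinine Clearance: As clinically indicated".

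At stake is the reading of one adverse event term in the secondary toxicity comparison. The primary PFS analysis is not affected.

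**Working it through.** The plan states no figure on this point, so there is none to reproduce. The check sets the schedules side by side, counts readings, and then asks how far a shortfall could move the planned comparison.

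**1. Scheduled clinic readings.** The inputs are item g of 4.3.2, a four-week cycle, and nivolumab once or twice per cycle.

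| | Arm A, two-weekly nivolumab | Arm A, four-weekly (adults only) | Arm C |
|---|---|---|---|
| Cycle 1 | 4 | 4 | 0 |
| Cycles 2 to 6 | 5 × 2 = 10 | 5 × 1 = 5 | 0 |
| First six cycles | 14 | 9 | 0 |
| All 26 cycles | 4 + 25 × 2 = 54 | 4 + 25 × 1 = 29 | 0 |

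These counts follow the wording of item g. As extracted, the Arm A map seems to limit the Day 15 checks in later cycles to patients under 18. That may be a PDF effect and was not used. Adult home readings on axitinib add 2 × 4 = 8 per cycle, or 48 in six cycles.

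**2. What Arm C does have.**
- A baseline at eligibility, the average of two readings (3.2.7.6), as in every arm.
- Physical exams (4.5.2 item a), at which pressure may be taken but is not required. In six cycles adults have 2 + 5 = 7 exams and children 4 + 5 = 9, the same as in Arm A.
- Advice in 4.1 to watch for hypertension during and just after each infusion, with no reading scheduled.

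**3. After cross-over.** Therapy follows Arm A (8.1), so item g applies by reference. It does not mention cross-over itself, and the restart of the cycle count is spelled out only for imaging and pharmacokinetics.

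**4. Illustration of the effect on the comparison.** The documents give no hypertension rate for either arm and no detection rate, so both are assumptions here. Suppose that both arms have the same true rate *p*, that Arm A records every case and that Arm C records a fraction *s*. The target of 28 patients at 1:1 gives 14 per arm. The recorded rates are then *p* and *p* × *s*. The chance of a significant result is the sum, over all counts *a* and *c*, of Bin(*a*; 14, *p*) × Bin(*c*; 14, *ps*) wherever the two-sided Fisher p-value is at most 0.05. The plan gives no level for this test, so 0.05 is also assumed.

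| *p* | *s* | Recorded difference | P(significant) | P with *s* = 1 |
|---|---|---|---|---|
| 10% | 75% | 2.5 points | 0.4% | 0.4% |
| 20% | 50% | 10 points | 3.5% | 1.6% |
| 30% | 50% | 15 points | 7.6% | 2.1% |
| 40% | 25% | 30 points | 31.5% | 2.0% |

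At 0.05 the test moves strongly only when the true rate and the under-recording are both high. At a two-sided level of 0.30, matching the plan's 70% intervals, it moves more: 19.4% against 11.7% in the second row, and 64.9% against 17.6% in the last.

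**The case against.** The strongest reply is that axitinib is the drug expected to raise blood pressure, so readings were placed where the risk is. Section 6.1 lists hypertension as likely (above 20%) with axitinib. Section 6.2 lists it for nivolumab only among events with insufficient evidence of causation. Arm C is not unobserved, since it has the exams and infusion visits above, and all Grade 3 or higher events are routinely reported (11.10). Only Grade 3 or higher events enter the comparison, and only one term in a very small trial is affected. All of this stands, and it limits the point. It does not explain why a list that claims to hold what the toxicity aim needs leaves the measurement out.

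A reader might go further and infer three things that the documents do not support.

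- *That the Arm A excess is inflated.* Closer monitoring can find Grade 3 events, but it can also prevent them. Adult readings of at least 140 systolic or 90 diastolic prompt treatment under 5.2.5.3, and Table 1 starts it at Grade 2. Elevated readings are also repeated the same day. The net direction is therefore unproven. Nor can a detection rate be worked out from reading counts, because the share of high readings is unknown and readings within a patient are not independent.
- *That a rise in hypertension at cross-over is guaranteed.* Informal measurement in Arm C is not zero measurement, and adding axitinib can itself raise pressure.
- *That the pediatric baseline goes stale because Arm C has no readings.* Section 5.2.5.1 fixes baseline at the enrollment exam. Added Arm C readings would not change that, and an Arm A patient's baseline ages in the same way.

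**Conclusion.** The omission is real. Over six cycles, Arm A has 14 or 9 scheduled clinic readings and Arm C has none, and adults on axitinib also have about 48 home readings. Hypertension rates by arm and after cross-over can therefore differ partly through ascertainment, and Section 9.3 does not say so.

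How much, and in which net direction, cannot be derived from the documents. It depends on how often pressure is taken at Arm C exams, on the true rates, and on how far early treatment in Arm A averts Grade 3 events. Any measurement effect will be mixed with an expected true axitinib effect. The equal-rate illustration shows sensitivity only and is not an estimate. On it, the distortion falls mainly on the reported rates rather than on the Fisher test at 0.05. This is an inexpensive improvement to a secondary comparison and does not threaten the primary result.

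**What to change.** Add blood pressure to the Arm C observation list (4.5.2) and delivery map (4.5.1) on Arm A's terms, as a study assessment: before each nivolumab dose and at the existing weekly Cycle 1 visits. Scheduled readings in Arm C then rise from 0 to 14 or 9 in six cycles (54 or 29 over 26), matching Arm A. A patient who crosses over then also has readings from before axitinib. The change concerns measurement only and leaves the management of hypertension as written.

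In Section 9.3, report the number of scheduled clinic readings per arm and in the cross-over group. State that hypertension comparisons are subject to unequal ascertainment. That caveat is needed even after the change, because patients already treated on Arm C cannot be measured again and adult home readings remain tied to axitinib.

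The cost is one list item, re-lettering of the Arm C list and map, and two sentences in 9.3. No visit is added, because Arm C patients already attend for blood tests on Days 8, 15 and 22 of Cycle 1 and for every infusion. The downside is a few extra readings at those visits. Scheduled counts follow from cycles started and doses given; counting readings actually taken would need a data field that the documents do not describe.
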